10.6. Detailed Description of the Pattern Mixture Model

As a sensitivity analysis of the primary neurocognitive endpoint (i.e. CANTAB cognitive domain SWM strategy z-score change from baseline to Week 96), a pattern-mixture model approach will be used to explore missing data patterns. Specifically, a different imputation strategy is planned for missing SWMS values during the TEAE period (i.e. within the time period from the first double-blind IMP injection up to the day of the last double-blind injection +70 days) in contrast to those missing after the TEAE period. Presented below are the reasons for considering differences in the impact of alirocumab dependent on the timing of the last study treatment administration:

- Patients who discontinued study treatment due to adjudicated neurocognitive events but are still within the TEAE period would continue to show impact from treatment similar to that observed for other patients who also had adjudicated neurocognitive events.

Note: The neurocognitive events recorded on the AE eCRF by the investigator are defined below, by any of the following programmatical procedures:

- Sponsor neurocognitive events CMQ;
- FDA neurocognitive events CMQ;
- Investigator identified NC events, as entered in the eCRF.

- Patients who discontinued study treatment due to reasons other than adjudicated neurocognitive events but are still within the TEAE period would continue to show impact from treatment similar to that observed for patients without any adjudicated neurocognitive events.
- Patients who discontinued study treatment (alirocumab or placebo) but are after the TEAE period would no longer be impacted by study treatment, and thus would have SWMS values similar to patients receiving placebo.

In addition, SWMS data missing prior to last study treatment administration (i.e., intermittent missing) are considered “Missing At Random”.

Missing SWMS values from the primary safety population will be imputed 100 times to generate 100 complete data sets. The change from baseline to Week 96 will be derived from observed and imputed SWMS at this time point. The completed data sets will be analyzed using an analysis of covariance (ANCOVA) model with treatment group and randomization strata as fixed effects, and the baseline SWMS value as continuous covariate. The results from the 100 analyses will be combined using Rubin’s formulae. If necessary, the number of imputations (100) will be increased until stable estimates are obtained.

Imputation Strategy 1: Missing data during the TEAE period for patients who discontinued study treatment due to adjudicated neurocognitive events

The imputation strategy for missing SWMS values following discontinuation of study treatment due to adjudicated neurocognitive events but still within the TEAE period, is to impute by patients who had at least one adjudicated neurocognitive event during the TEAE period.

Specifically, data collected during the TEAE period for patients who had at least one adjudicated neurocognitive event during the TEAE period will be used to impute missing data.

For each patient, missing SWMS values will be imputed 100 times, using a random draw from a normal distribution, with mean equal to the mean of the observed SWMS values, and variance equal to the conditional variance of observed SWMS values given the baseline value, at the specific time-point from patients in the same treatment group who had adjudicated neurocognitive events during the TEAE period.

Let Y_0 and Y_1 denote the SWMS at baseline and at the specific time-point respectively. Since Y_0 and Y_1 are assumed to have a bivariate normal distribution, the conditional variance of Y_1 given Y_0 is:

$$Var(Y_1|Y_0 = y_0) = \sigma_1^2(1 - \rho^2)$$

Where σ_1^2 denotes the variance of Y_1 and ρ the coefficient of correlation between Y_0 and Y_1 .

During the random generation process, a minimum value of 4 and a maximum of 28 will also be applied in order to avoid imputed SWMS values out of range.

Imputation Strategy 2: Imputation of missing data during the TEAE period for patients who discontinued study treatment due to reasons other than adjudicated neurocognitive events

The imputation strategy for missing SWMS values following discontinuation of study treatment due to reasons other than adjudicated neurocognitive event, but still within the TEAE period, is to impute by patients who did not have any adjudicated neurocognitive events during the TEAE period. Specifically, data collected during the TEAE period for patients who did not have any adjudicated neurocognitive events during the TEAE period will be used to impute missing data.

For each patient, missing SWMS values will be imputed 100 times, using a random draw from a normal distribution, with mean equal to the mean of the observed SWMS values, and variance equal to the conditional variance of observed SWMS values given the baseline value, at the specific time-point from patients in the same treatment group who did not have any adjudicated neurocognitive events during the TEAE period.

Let Y_0 and Y_1 denote the SWMS at baseline and at the specific time-point respectively. Since Y_0 and Y_1 are assumed to have a bivariate normal distribution, the conditional variance of Y_1 given Y_0 is:

$$Var(Y_1|Y_0 = y_0) = \sigma_1^2(1 - \rho^2)$$

Where σ_1^2 denotes the variance of Y_1 and ρ the coefficient of correlation between Y_0 and Y_1 .

During the random generation process, a minimum value of 4 and a maximum of 28 will also be applied in order to avoid imputed SWMS values out of range.

Imputation of missing data after the TEAE period

The imputation strategy for missing SWMS values following discontinuation of study treatment, and after the TEAE period, is to impute by patients who are in the placebo treatment group. Specifically, all data collected (whether during TEAE period or after TEAE period) for patients who are in the placebo treatment group will be used to impute missing data.

For each patient, missing SWMS values will be imputed 100 times, using a random draw from a normal distribution, with mean equal to the mean of the observed SWMS values, and variance equal to the conditional variance of observed SWMS values given the baseline value, at the specific time-point from patients in the placebo treatment group.

Let Y_0 and Y_1 denote the SWMS at baseline and at the specific time-point respectively. Since Y_0 and Y_1 are assumed to have a bivariate normal distribution, the conditional variance of Y_1 given Y_0 is:

$$Var(Y_1 | Y_0 = y_0) = \sigma_1^2(1 - \rho^2)$$

Where σ_1^2 denotes the variance of Y_1 and ρ the coefficient of correlation between Y_0 and Y_1 .

During the random generation process, a minimum value of 4 and a maximum of 28 will also be applied in order to avoid imputed SWMS values out of range.

Signature Page for VV-RIM-00109809 v1.0

ESig Approval

ESig Approval

ESig Approval

ESig Approval

ESig Approval

Signature Page for VV-RIM-00109809 v1.0 Approved

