2.2. Sample Size and Power Considerations

To demonstrate the noninferiority of the Praluent 75 mg Q2W/up-titrate 150mg Q2W dose regimen relative to placebo for the primary endpoint of mean change in Spatial Working Memory (SWM) strategy z-score from baseline to week 96, the sample size for this study is calculated to be 1085 patients per treatment group. This sample size is based on the noninferiority margin of 0.2 for the primary outcome measure. Specifically, a worsening in the SWM strategy z-score of 0 to 0.2 at the group level (small effect size) would not be considered clinically meaningful. Whereas a worsening of 0.3 to 0.5 (or greater), a small-to-medium effect size, might be considered clinically relevant, indicating increased cognitive impairment (Roiser 2015). Therefore, a noninferiority margin of 0.2 on the SWM strategy z-score change from baseline is a conservative estimate of the largest clinically meaningless mean difference between Praluent and placebo treatment groups. Additionally, the assumed mean difference between the treatment groups is 0 and the standard deviation is 1.0 (the standard deviation is obtained from the Cambridge Cognition internal normative data). To achieve 95% power using a 2-sided 95% confidence interval (CI) approach (2-sided alpha=0.05), the sample size is calculated to require 651 patients per treatment group. Assuming dropout rate of 20% in the first year and 25% in the second year, the sample size is increased to 1085 patients per treatment group.

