The MMRM model relies on the “missing-at-random” (MAR) assumption. Because the possibility for a not-missing-at-random (NMAR) missingness mechanism can never be excluded, sensitivity analysis to explore the impact of non-ignorable missingness on the primary neurocognitive endpoint analysis will be conducted using the pattern mixture model approach as described below (see Appendix 10.6 for more details).

In the pattern-mixture model approach, different imputation strategies will be applied to the primary neurocognitive endpoint (i.e. CANTAB cognitive domain SWM strategy z-score change from baseline to Week 96) values missing during TEAE period (i.e. within the time period from the first double-blind IMP injection up to the day of the last double-blind injection +70 days) in contrast to those missing after the TEAE period. Presented below are the reasons for considering differences in the impact of alirocumab dependent on the timing of the last study treatment administration:

- Patients who discontinued study treatment due to adjudicated neurocognitive events but are still within the TEAE period would continue to show impact from treatment similar to that observed for other patients who also had adjudicated neurocognitive events.

Note: The neurocognitive events recorded on the AE eCRF by the investigator are defined below, by any of the following programmatical procedures:

- Sponsor neurocognitive events CMQ;
- FDA neurocognitive events CMQ;
- Investigator identified NC events, as entered in the eCRF.
- Patients who discontinued study treatment due to reasons other than adjudicated neurocognitive events but are still within the TEAE period would continue to show impact from treatment similar to that observed for patients without any adjudicated neurocognitive events.
- Patients who discontinued study treatment (alirocumab or placebo) but are after the TEAE period would no longer be impacted by study treatment, and thus would have SWMS values similar to patients receiving placebo.

Missing data from the primary safety population will be imputed 100 times to generate 100 complete data sets, using the approach described above. The 100 completed datasets of

observed and imputed LDL-C data will be used for primary neurocognitive endpoint analyses.

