10.5. Detailed Description of the Multiple Imputation Procedure

The following is a detailed description of the multiple imputation procedure which will be used for sensitivity analysis of primary endpoint as well as the analysis of the secondary endpoints.

In general, the missing pattern is anticipated to be not monotone, a two-step approach will be used:

- Step 1: the MCMC method will be used in conjunction with the IMPUTE=MONOTONE option to create an imputed data set with a monotone missing pattern.

- Step 2: Using the monotone data set from step 1, missing data will be imputed using the regression method.

The imputation model for step 1 will include the treatment group and the values of the analyzed parameter at baseline and planned time-points up to week 96.

The imputation model for step 2 will include the same variables as in step 1 with the following additional variables:

- the randomization strata (age and statin use strata);
- age, BMI, and gender (age and BMI included as continuous variables).

Non-continuous variables included in the imputer's model (i.e., treatment group, randomization strata and gender) are not expected to be missing.

In addition, for continuous efficacy variables anticipated to have a non-normal distribution (i.e. TG and Lp(a)), data will be log-transformed before imputation process and then back-transformed to create the imputed data sets using the TRANSFORM statement of SAS MI procedure.

For variables other than those continuous efficacy variables anticipated to have a non-normal distribution (i.e. TG and Lp(a)), for each simulation leading to negative imputed value, another value will be redrawn using MINIMUM option of MI SAS procedure.

The number of imputations (100) will be informally verified by replicating sets of 100 imputations and checking whether the combined results are stable. If not stable, the number of imputations will be increased and informally checked as above, and thus continued until stable estimates are obtained.

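### The pattern-mixture imputation combines an unconditional mean with a baseline-conditional variance, so the SAP's only not-missing-at-random check can be biased in either direction

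*SAP*

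**What the plan says.** SAP 5.6.1.2 notes that the MMRM relies on missing at random, and therefore plans that "sensitivity analysis to explore the impact of non-ignorable missingness on the primary neurocognitive endpoint analysis will be conducted using the pattern mixture model approach". SAP 10.6 defines three imputation patterns:

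- Strategy 1: missing within the TEAE period after stopping for an adjudicated neurocognitive event. Donors are same-arm patients with such events.
- Strategy 2: missing within the TEAE period after stopping for another reason. Donors are same-arm patients without such events.
- Missing after the TEAE period: donors are placebo patients, for both arms.

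In each pattern the draw has "mean equal to the mean of the observed SWMS values, and variance equal to the conditional variance of observed SWMS values given the baseline value". The section assumes that baseline Y₀ and the later score Y₁ are bivariate normal and prints the variance σ₁²(1−ρ²). It gives no formula for a conditional mean, and y₀ does not enter the mean. Baseline appears only afterwards, as the ANCOVA covariate. By contrast, the first-step model of the multiple imputation in SAP 10.5 "will include the treatment group and the values of the analyzed parameter at baseline and planned time-points up to week 96".

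**The concern.** The stated mean and variance do not belong to one distribution unless ρ = 0. A patient who enters the trial well below average and then drops out is imputed as an average patient. If the patients lost from one arm were worse at baseline than those lost from the other, that arm is credited with an improvement that nobody observed.

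Noninferiority is declared from the MMRM, so the primary conclusion does not rest on this rule. What is at stake is the support for it: agreement or disagreement between the pattern-mixture result and the MMRM could be produced by the formula rather than by the missing data.

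**Working it through.** **Inputs from the plan.** The margin is 0.2 and the SD 1.0 ("the assumed mean difference between the treatment groups is 0 and the standard deviation is 1.0"). SAP 2.2 reproduces: 2 × (1.960 + 1.645)² / 0.2² = 649.7, so 650 by the normal approximation and 651 with the t distribution, as stated. Retention is 0.80 × 0.75 = 0.60 ("Assuming dropout rate of 20% in the first year and 25% in the second year"), and 651 / 0.60 = 1085. The planning fraction missing at week 96 is therefore m = 0.40. It is an upper figure, because the primary safety population requires at least one score during the TEAE period.

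**Assumptions, not in the documents.** ρ (0.6 unless stated), how dropout depends on baseline, and the share of imputations using placebo donors. For that share: week 96 is day 673, and 673 − 70 = 603, which is week 86. If stops were spread evenly over 94 weeks, 86/94 = 91% would be past the TEAE period at week 96; 90% is used below.

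**The mismatch.** Given y₀, bivariate normality implies
- mean μ₁ + ρ(σ₁/σ₀)(y₀ − μ₀)
- variance σ₁²(1−ρ²)

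Ignoring y₀, it implies mean μ₁ and variance σ₁². The SAP takes the mean from the second pair and the variance from the first. At ρ = 0.6 a patient 2 SD worse than the donors at baseline should be imputed 0.6 × 2 = 1.2 SD worse on average, but is imputed at the donor average. With 40% missing, the baseline to week-96 correlation in the completed data falls from 0.60 to 0.36/√(0.6 + 0.4 × 0.64) = 0.39.

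**Bias by formula.** Let g be the baseline mean of missing minus observed patients in an arm, in SD (T Praluent, C placebo), with equal m.
- Same-arm donors: bias = −mρ(g_T − g_C). With g_T = 0.32 and g_C = 0: −0.4 × 0.6 × 0.32 = −0.077. Simulated trials of 1085 per arm with a true difference of 0.20 gave a mean estimate of 0.123. The mirror case gave 0.280. The conditional mean gave 0.200 in both.
- Placebo donors for both arms: bias = −mρ(1−m)(g_T − g_C). With g_T = 0.161: −0.4 × 0.6 × 0.6 × 0.161 = −0.023. Simulation gave −0.023, and +0.024 in the mirror case.

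**Large-sample simulation.** 1.5 million per arm, no true difference, ANCOVA on treatment and baseline, ρ 0.6, 90% placebo donors. Slopes are log-odds of dropout per SD of worse baseline, Praluent/placebo.

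| Slopes | Missing | Bias, SAP rule |
|---|---|---|
| 0.1/0 | 40% | −0.015 |
| 0.25/0 | 40% | −0.038 |
| 0.5/0 | 40% | −0.072 |
| 0/0.25 | 40% | +0.038 |
| 0/0.5 | 40% | +0.073 |
| 0.25/0 | 20% | −0.024 |
| 0.5/0 | 20% | −0.047 |
| 0.5/0.5 | 40% both | 0.00 |
| 0.5/0.5 | 45% v 35% | −0.017 |
| 0.5/0.5 | 35% v 45% | +0.020 |

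The conditional mean gave 0.00 in every case. For slopes 0.25/0 and 0.5/0 at 40% missing, the SAP rule gave −0.025 and −0.048 at ρ 0.4, and −0.050 and −0.097 at ρ 0.8. At ρ = 0 the bias is 0.00.

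Cross-check on 0.5/0: with placebo donors only, the simulated bias is −0.068, so g_T = 0.068/(0.4 × 0.6 × 0.6) = 0.47. Same-arm donors would then give −0.4 × 0.6 × 0.47 = −0.113. The 90/10 mix is −(0.9 × 0.068 + 0.1 × 0.113) = −0.0725, which agrees.

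**With a true on-treatment difference of 0.2.** The value 10.6 aims at, placebo-like after the TEAE period, is 0.2 × (1 − 0.4 × 0.9) = 0.128. The SAP rule gave 0.056 (0.5/0), 0.090 (0.25/0), 0.166 (0/0.25) and 0.201 (0/0.5). The conditional mean gave 0.127 to 0.128 throughout.

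Truncation at 4 and 28 was not modelled, because the raw-score SD is not given.

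**The case against.** The strongest reply is that a pattern-mixture model states an untestable assumption, and 10.6 states its assumption by level: after the TEAE period, patients score like placebo patients. On that reading the donor mean is intended and the variance is the slip; it should be σ₁². This does not rescue the rule. Raising the variance leaves the bias unchanged and still makes imputed scores unrelated to a baseline for which the ANCOVA then adjusts. The SAP nowhere argues that dropouts revert to the donor average whatever their starting point.

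Other points have more force:

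- **Size.** The larger figures need baseline-related dropout in one arm only. The trial is double-blind, with lipid results and dose changes masked, and the documents give no reason to expect this. Symmetric selection gives zero at equal rates and about a tenth of the margin with a 10-point difference in dropout.
- **Amount missing.** Protocol 7.3.1 and 7.3.1.2 ask patients who stop study drug to stay in the study and return at week 96. If those off-drug scores are kept in this analysis, on which the SAP is not explicit, fewer values need imputing.
- **Diagnostics.** SAP 5.6.1.2 plans plots of mean score, including baseline, by missing-data pattern and arm. These would reveal an imbalance but not correct the estimate.
- **Role.** This is one of the supportive analyses, with no decision rule attached.

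These points limit the consequence; they do not make the formula right.

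**Conclusion.** The concern holds. The rule is wrong as written, not merely short of detail, and nothing elsewhere in the SAP supplies a conditional mean. Bias in the treatment difference is possible rather than inevitable, and its sign depends on which arm loses the worse-baseline patients. Under the stated assumptions, one-arm selection at 40% missing moves the estimate by 0.015 to 0.073, or about 8% to 36% of the 0.2 margin; the effect is smaller with less missing data and nil under matched dropout.

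Confidence is high on the mismatch. The magnitudes depend on the assumed ρ, dropout slopes and donor share. The primary MMRM and the multiple-imputation ANCOVA are not affected. This should be fixed before database lock because it is the plan's only not-missing-at-random analysis.

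**What to change.** In all three patterns, set the mean of the draw to μ₁ + ρ(σ₁/σ₀)(y₀ − μ₀), with every term estimated in the donor group. Keep the stated variance and the 4 to 28 limits. In the placebo-donor step, condition on baseline alone and not on interim scores, so that the assumption of no remaining treatment effect is preserved. Preferably draw the donor parameters afresh for each imputation: with same-arm donors and ρ 0.6, fixed parameters still left Rubin's standard error slightly small after the correction (0.041 against an empirical 0.045).

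The cost is one formula in three places and a small program change. SAP Section 1 allows revision before lock.

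The drawback is in Strategy 1, where donors may be few. With 10 donors and ρ 0.6, the SD of the imputed mean for a patient 1 SD above average is √[0.64 × (1/10 + 1.1/7)] = 0.41 using the group's own slope, and √(0.64/10) = 0.25 using a well-estimated pooled slope. Pooling the slope across donor groups is therefore sensible if that group is small, on the assumption that the slope is the same with and without neurocognitive events.

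Two wording corrections can be made at the same time: state that results are reported in z-score units, comparable with the margin, and replace the stray reference to LDL-C data in the pattern-mixture text of 5.6.1.2 with SWMS.

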5.6.1.2. Sensitivity to the Handling of Missing Data

Sensitivity analyses will be conducted to assess the robustness of primary analysis with regards to handling of missing data (3).

Visual examination:

- In order to explore the missing data pattern, post-baseline SWM strategy z-score observations during the TEAE period (in the primary safety population) will be described according to the following groups:
 - SWM strategy z-score available at week 96 (i.e. primary endpoint available),
 - SWM strategy z-score available at week 72 but missing at week 96,
 - SWM strategy z-score available at week 48 but missing from week 72,
 - SWM strategy z-score available at week 24 but missing from week 48,
 - SWM strategy z-score missing from week 24.

A graph of mean SWM strategy z-score (respectively change from baseline in SWM strategy z-score) \pm SE at baseline, and weeks 8, 12, 24, 48, 72, and week 96 will be provided by missing data pattern, for each treatment group.

- In the primary safety population, demographic and baseline characteristics will be described within the missing data pattern number 1 versus the pooled others. P-values from Chi-square test for categorical data and from asymptotic one-way ANOVA test for Wilcoxon scores (Kruskal-Wallis test) for continuous data, will be also provided, for descriptive purposes.

Multiple Imputations:

In addition to the MMRM method, the multiple imputation method (see Appendix 10.5 for more details) will be used to address missing values, in the primary safety population, followed by the testing of treatment arms using an analysis of covariance (ANCOVA) model, with the intent to evaluate the robustness of the primary analysis using a different statistical method.

Missing data from the primary safety population will be imputed 100 times to generate 100 complete data sets, using the MI SAS procedure (using Markov Chain Monte Carlo). The

percent change from baseline at week 96 will be then derived from observed and imputed SWM strategy z-score at this time point. The 100 complete data sets will be then analyzed using an ANCOVA model with treatment group and randomization strata (as per IVRS/IWRS) as fixed effects, and the baseline SWM strategy z-score as continuous covariate, and the MIANALYZE procedure will be used to generate valid statistical inferences by combining results from the 100 analyses using Rubin's formulae (4).

Pattern mixture model:

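### The only analysis that departs from missing at random sets late-missing Praluent scores to the placebo mean, so it cannot show those patients doing worse

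*SAP*

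**What the plan says.** SAP 5.6.1.2 notes that the MMRM relies on missing at random and that other mechanisms cannot be excluded. It then states that "sensitivity analysis to explore the impact of non-ignorable missingness on the primary neurocognitive endpoint analysis will be conducted using the pattern mixture model approach".

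SAP 10.6 divides missing scores by timing:

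- **Within the TEAE period (last dose + 70 days).** Strategy 1 is headed "Missing data during the TEAE period for patients who discontinued study treatment due to adjudicated neurocognitive events". Strategy 2 covers patients who stopped for other reasons. Both draw from patients in the same treatment group.
- **After the TEAE period.** The strategy for scores missing "following discontinuation of study treatment, and after the TEAE period, is to impute by patients who are in the placebo treatment group". The donors are "all data collected (whether during TEAE period or after TEAE period) for patients who are in the placebo treatment group". The draw is normal, "with mean equal to the mean of the observed SWMS values" at that time point. The stated reason is that these patients, on either treatment, "would no longer be impacted by study treatment, and thus would have SWMS values similar to patients receiving placebo".

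The other missing-data work in SAP 5.6.1.2 is multiple imputation without any shift (details in 10.5) and graphs of mean scores that "will be provided by missing data pattern, for each treatment group". The summary table in SAP 10.1 adds only a rerun with actual strata. Neither document has a delta-adjusted, tipping-point or worse-than-placebo analysis of the scores.

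**The concern.** A higher score is worse, and noninferiority needs an upper 95% limit below 0.2. If the observed Praluent patients do worse than placebo, adding patients whose difference is zero by construction pulls the estimate toward noninferiority. If the observed Praluent patients do better, the rule pulls toward placebo, but it never places the missing patients below it. The scenario a safety trial most needs to examine is therefore ruled out for this group.

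Two features sharpen the point:

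- A Praluent patient who stopped because of an adjudicated neurocognitive event is also given placebo-based values once 70 days have passed.
- The draw ignores the patient's own earlier scores. A worsening recorded by the battery at discontinuation (Protocol Table 1 footnote 8 and 7.3.1) can move the MMRM but not this analysis.

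At stake is the weight of a statement that the result is robust to missing data. For these patients the analysis assumes the answer.

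A related gap is whether week 96 scores observed after the TEAE period are used. SAP 10.6 says "The change from baseline to Week 96 will be derived from observed and imputed SWMS at this time point" and lets placebo donors supply post-TEAE scores, while SAP 4.6.1 limits the week 96 score to the TEAE period.

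**Working it through.** **Plan's own figures.** Inputs from SAP 2.2: margin 0.2, SD 1.0, true difference 0, power 95%, two-sided 95% CI. The normal approximation 2 × (1.96 + 1.645)² / 0.2² gives 650 per arm, and the t-based version gives 651, as stated. Dropout of 20% then 25% leaves 0.80 × 0.75 = 0.60, and 651 / 0.60 = 1085, as stated.

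**Who is affected.** The week 96 target is day 673 and its window opens on day 589 (SAP 10.2, Table 2). The score falls after the TEAE period if the last dose was before day 673 − 70 = 603 (about week 86), or before day 589 − 70 = 519 (about week 74) if judged at the window start.

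**Share f of the Praluent arm imputed from placebo.** The documents do not give f. Assume that dropout means drug stopped and score absent, with constant hazard within each year.

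- 48-week years (336 days): loss by day 519 = 1 − 0.80 × 0.75^(183/336) = 0.316. By day 603 it is 1 − 0.80 × 0.75^(267/336) = 0.363.
- Calendar years: 0.291 and 0.337.
- The primary safety population needs a score in the TEAE period. Patients stopping before day 169 − 70 = 99 would have no scheduled week 24 score in it: 1 − 0.80^(99/336) = 0.0636 (calendar 0.0587). That leaves 1016-1021 of 1085 per arm.
- f = (0.316 − 0.0636) / 0.9364 = 0.270, and (0.363 − 0.0636) / 0.9364 = 0.320. Calendar years give 0.247 and 0.296.
- So f is about 0.25-0.32, or 0.12-0.16 if half of these patients return at week 96 and their scores are kept.

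**Expected estimate.** With a uniform true harm d that fully persists, the estimate is (1 − f) × d + f × 0. For d = 0.20 this is 0.150 at f = 0.25 and 0.136 at f = 0.32. With half returning, it is 0.176 at f = 0.12 and 0.168 at f = 0.16.

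**How often this analysis meets the margin.** Simulation with draws as in SAP 10.6, 100 imputations, ANCOVA, Rubin's rules and about 1018 per arm. The correlation of 0.5 is chosen because √(2(1 − 0.5)) = 1.0, the planned SD.

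| True overall harm and scenario | Margin met |
|---|---|
| 0.20, fully persistent, f 0.25-0.32 | about 14-23% |
| same, half return (f 0.12-0.16) | about 5-10% |
| same as first row, correlation 0.3 | 12-17% |
| same as first row, correlation 0.7 | 20-32% |
| 0.20, stopped patients keep half the harm | about 4-7% |
| 0.25 | 2-4% |
| 0.30 | about 0.2% or less |

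At a true difference of 0 the mean estimate is 0.00.

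Hand check with 1085 per arm and f = 0.30: simulated mean 0.140, Rubin standard error 0.0436, actual spread 0.0326. (0.2 − 1.96 × 0.0436 − 0.140) / 0.0326 = −0.78, a probability of about 0.22, against 0.228 simulated.

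**When harm sits in the missing patients.** As an illustration with assumed values, Praluent patients with a week 96 score differ by 0.05 and the missing 36% by 0.47. The overall harm is 0.64 × 0.05 + 0.36 × 0.47 = 0.20. The MMRM was simulated with on-treatment scores and the battery at stopping included, strata omitted. If none, a quarter or half of the extra worsening shows at the last on-treatment score, the MMRM meets the margin in about 89-91%, 84-88% or 75-78% of trials. The pattern mixture model meets it in 96-99%, and reverses 5 of 6,066 MMRM passes (4 of 1,767, 1 of 2,540 and 0 of 1,759). In those passes a tipping-point analysis would lose noninferiority at a median penalty of about 0.17-0.21, roughly half of the simulated excess of 0.42.

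**The case against.** The strongest reply is that this analysis decides nothing. Under a uniform harm of 0.20 the MMRM is correctly specified: a missing-at-random analysis passed in only about 2-4% of simulated trials. The pattern mixture model only supports an MMRM pass, so it adds no false conclusion there. That stands: 14-23% is a property of one sensitivity analysis and not a trial-level error rate. It does not answer the case where harm is concentrated in the missing patients, which is why the analysis exists.

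The size also depends on assumptions. Protocol 7.3.1 and 7.3.1.2 ask patients who stop drug to keep attending, at least at week 96. Harm may fade, and the true value may not sit at the margin. All of this lowers the figures, as the table shows. The 0.05 and 0.47 are illustrative, and the visible share was not taken above one half. In the other direction, the battery at stopping could qualify early stoppers for the primary safety population, which would raise f.

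Washout is a reasoned choice: SAP 4.7.1 expects residual effect for 10 weeks. But that is a statement about the drug. Neither document shows that a cognitive harm would reverse in that time.

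Adjudicated neurocognitive events, Kaplan-Meier summaries and events leading to discontinuation would also carry information. They do not replace an analysis of the score. Finally, no analysis can test unseen scores, and a tipping point has no automatic pass or fail. It does show how much worse the missing patients would have to be, which the present plan never shows.

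**Conclusion.** The concern holds and should be fixed before lock. SAP 10.6 fixes the expected difference at zero for every Praluent patient whose week 96 score is missing after the TEAE period, and no other formal planned analysis departs from missing at random. By itself it cannot support a claim of robustness to non-ignorable missingness.

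The distortion is material if harm persists after stopping and few of these patients return, and modest if half return or half the harm fades. There is none if the effect washes out as the SAP assumes or if there is no harm. The figures rest on planning dropout standing for absent scores, on the assumed hazard and correlation, and on simplified simulations. The mechanism follows from the SAP text alone.

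**What to change.** Before database lock, amend SAP 5.6.1.2, 10.1 and 10.6:

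1. Add a delta-adjusted tipping-point analysis. Impute missing Praluent week 96 scores from their own arm plus a penalty of 0, 0.1, 0.2, 0.3 and so on in z-score units, with no penalty for placebo. Report the smallest penalty at which the upper 95% limit reaches 0.2, and read it against the 0.3-0.5 that SAP 2.2 says might be clinically relevant. For orientation, with no observed difference and the planned half-width 1.96 × √(2/651) = 0.109, the tipping penalty is about (0.2 − 0.109) / f, or 0.30 when f = 0.30.
2. For patients who stopped because of an adjudicated neurocognitive event, keep event-based imputation after the TEAE period. If same-arm event donors are too few, which is likely given the low incidence noted in Protocol 1.1, use own-arm imputation plus a penalty. Few patients are affected, so this changes less than item 1.
3. Keep the placebo-based version, labelled as a washout scenario.
4. State whether week 96 scores observed after the TEAE period enter this analysis, and reconcile that with SAP 4.6.1.

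The cost is SAP wording and a few more runs of code already planned. Protocol 9.5.2.1 leaves the sensitivity analyses to the SAP, so no protocol amendment is needed. The sensitivity result may look less favourable.
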